11.2 Phase II

The primary objective of the phase II is to evaluate the efficacy of the combination in patients with FLT3-ITD mutated AML (n=20). The primary endpoint is the rate of CRc (CRc=CR/CRp/CRi) at any time during the first three cycles of therapy. The CRc will be monitored with a time window of 3 months, and toxicity will be monitored as DLT within 1 cycle of the treatment. CRc and toxicity will be monitored simultaneously using the Bayesian approach of Thall, Simon, Estey (1995, 1996) as extended by Thall and Sung (1998).

Of note, recent FDA approval of midostaurin in combination with 7+3 induction chemotherapy in newly diagnosed FLT3-mutant AML signifies that essentially all relapsed FLT3-mutated AML patient will likely have been exposed to at least one FLT3 targeting TKI. In this setting, the marrow response (CRc) rates with second generation FLT3 inhibitors such as crenolanib, gilteritinib and quizartinib have been reported to be lower than in prior FLT3 TKI naïve patients and are in the range of 20-25% (26, 48, 49) and Daiichi Sankyo unpublished communication).

Thus, the historical data suggested a CRc rate of 25% for this population with quizartinib alone and the target CRc with the quizartinib and venetoclax combination is 50%. The treatment will be considered worthy of further investigation if it elicits an increase in CRc to 50% or higher with acceptable toxicity. A >30% DLT rate is considered unacceptable. Given this, we will stop enrollment into this cohort if the observed patients' data suggest that:

- 1) $\Pr(\text{CRc}_E > \text{CRc}_H + 0.25 | \text{data}) < 0.025$ or
- 2) $\Pr(\text{TOX}_E > 0.30 | \text{data}) > 0.90$

Here CRc_E and CRc_H are the CRc rate for quizartinib in combination with venetoclax and the historical treatment, respectively. TOX_E is the toxicity rate for quizartinib in combination with venetoclax, where the toxicity is defined as the DLTs. That is, if at any time during the study we determine that there is a less than 2.5% chance that the average CRc rate improves over historical CRc rate by more than 25% we will stop enrollment to this cohort. The second condition will stop the study early if there is more than 90% chance that the toxicity rate is more than 30%. The CRc_E and CRc_H are assumed to follow a prior of Beta (0.5, 1.5) and a constant of 25%, respectively. The stopping boundaries for CRc, based on these assumptions and monitoring conditions are found in **Table 4**. We will apply these stopping boundaries continuously starting from the tenth patient in a cohort size of 5 patients. For example, accrual will cease if less than or equal to 2 patients experience CRc among the first 10 patients treated.

Table 4. Stopping boundaries for CRc rate.

Stop accrual if the number patients with CRc among the number of patients evaluated			
Number of patients evaluated for CRc	10	15	20
Number of patients with CRc (i.e., CR, CRp, or CRI) is less than or equal to	0-2	0-4	Always stop with this many patients

Similarly, for monitoring the toxicity, a beta (0.6, 1.4) prior and a constant 30% toxicity rate were assumed for the historical treatment and the experimental combination, respectively. Based on these assumptions and monitoring conditions, the stopping boundaries for toxicity were generated and summarized in **Table 5**. For toxicity monitoring, we will apply these stopping boundaries continuously starting from the fifth patient in a cohort size of 5 patients. For example, accrual will cease if 4 or more patients experience toxicities among the first 5 patients.

For accrual between cohorts, if there are enough evidence indicating that the number of patients with CRc will be greater than that of the stopping boundaries (i.e., 2/10 or 4/15), it will continue; while will be held for evaluations of all patients if this cannot yet be determined with currently available data. Same strategy will be also applied to the toxicity monitoring.

Table 5. Stopping boundaries for Toxicity

Stop accrual if the number of patients with DLTs among the number of patients evaluated				
# patients evaluated	5	10	15	20
# patients with toxicities	4-5	6-10	8-15	Always stop with this many patients

The operating characteristics are summarized in Table 6. The probability of stopping the study early if the true CRc of the combination treatment was 50% and the true toxicity rate was 30% was 16.1%. Probabilities of stopping early for high true toxicity rates (i.e., 50%) were 59.5% when the true CRc was 50% and 56.2% when true CRc rate was 65%.

Table 6. Operating characteristics for simultaneous monitoring response and toxicity rates for patients treated with combination treatment

True Toxicity Rate	True CRc	Prob(stop the trial early)
0.10	0.25	0.7188
	0.35	0.3976
	0.50	0.0837
	0.60	0.0177
	0.65	0.0069
0.20	0.25	0.7223
	0.35	0.4052
	0.50	0.0952
	0.60	0.0301

Table 6. Operating characteristics for simultaneous monitoring response and toxicity rates for patients treated with combination treatment

True Toxicity Rate	True CRc	Prob(stop the trial early)
0.30	0.65	0.0194
	0.25	0.7424
	0.35	0.4481
	0.50	0.1605
	0.60	0.1001
	0.65	0.0902
0.40	0.25	0.7956
	0.35	0.5621
	0.50	0.3340
	0.60	0.2860
	0.65	0.2782
0.50	0.25	0.8758
	0.35	0.7340
	0.50	0.5955
	0.60	0.5663
	0.65	0.5616

If the study is not stopped early and 20 patients have been treated and evaluated in the study, a 95% credible interval around the CRc under the combination treatment will be no wider than 41%. The in-house Multc Lean Desktop (version 2.1.0) was used to generate the toxicity and futility stopping boundaries, and the Parameter Solver (version 3.0.0) was used to construct the credible intervals.

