1.0 OBJECTIVES

1.1 Primary Objectives

Phase Ib

1. To determine the maximum tolerated dose (MTD) and the recommended phase 2 dose (RP2D) of the combination of venetoclax with quizartinib in FLT3-ITD mutated patients with relapsed/refractory acute myeloid leukemia (AML).

Phase II

1. To determine the composite CR (CRc) rate including CR (complete remission) + CRp (complete remission with incomplete platelet recovery) + CRI (complete remission with incomplete count recovery) within 3 months of treatment initiation in FLT3-ITD mutated patients with relapsed/refractory AML.

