It is suggested that each dose of venetoclax be taken with approximately 240 mL of water within 30 minutes after the completion of a low-fat breakfast. Examples of a low-fat breakfast include 2 slices of white toast with 1 tablespoon of low-fat margarine and 1 tablespoon of jam, and 8 ounces/240 mL of skim milk (319 calories and 8.2 g fat) or 1 cup/30 g of cereal, 8 ounces/240 mL of skim milk, 1 slice of toast with jam, 1 cup/240 mL of apple juice, and 1 cup/240 mL of coffee or tea (520 calories and 2 g fat). If vomiting occurs within 15 minutes after taking venetoclax and all expelled tablets are still intact, another dose may be taken. Otherwise, no replacement dose is to be taken. In cases where a dose of venetoclax is missed or forgotten, the patient should take the dose as soon as possible, ensuring that the dose is taken with food within 8 hours after the missed dose. Otherwise, the dose should not be taken. Patient compliance with the assigned daily dose of venetoclax will be assessed by standard pill counts. Bottles containing venetoclax tablets will be given to patients at regular scheduled visits. Previously distributed bottles will be returned to the clinic and tablets counted and returned study drug destroyed per institutional policy. Any discrepancy will be resolved with the patient at each clinic visit and documented in the patient record.

Any overdose or incorrect administration of Venetoclax and Quizartinib should be noted within Prometheus. Adverse events associated with an overdose or incorrect administration of study drug should be recorded as an Adverse Event within Prometheus.

- 5.1.1.1 Cycles may be started early (but not earlier than day 21) for patients with active disease if judged in the best interest of the patient.

*For the phase Ib, DLT defining period is 28 days. As such, cycle 2 should not be started before 28 days for the patients being treated on the phase Ib cohort to allow for adequate evaluation of DLTs.

- 5.1.1.2 Subsequent cycles may be delayed for recovery of toxicity or other medical conditions. Delays in start of subsequent cycles greater than 8 weeks will be acceptable only for patients who are deriving clinical benefit and after discussion with the principal investigator and the sponsor of potential risk/benefit ratio and complete documentation of the degree of clinical benefit and reason for continuation on this regimen.

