8.0 CRITERIA FOR RESPONSE

Response criteria will be modified from the International Working Group for AML(52). Responders are patients who obtain a Composite Complete Remission Rate (CRc) with or without cytogenetic response, hematologic improvements, and morphologic leukemia-free state. CRc rate is defined as the confirmed remission rate of all complete and incomplete CRs (i.e., CR+ CRp + CRi).

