8.8 Best Response measurement

Response will be measured and defined for primary endpoints as the best response achieved during the first 3 cycles of therapy, or at time off study, for those patients discontinuing treatment before the completion of 3 cycles of therapy. Best response is defined to be the best-measured response (CRc=CR+CRp+CRi, PR, or marrow clearance) post-treatment up to that time. Best response will also be evaluated for the full treatment period using all assessments up to and including treatment discontinuation.

9.0 DISCONTINUATION OF TREATMENT:

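### The Phase II primary endpoint, CRc, is defined inconsistently on time window, confirmation and early leavers, so the same patient can count as a responder or a failure

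*Combined protocol and SAP*

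**What the plan says.** Three features of the endpoint are stated more than one way in the current text.

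- **Window.** The Phase II primary objective (1.1) is the CRc rate "within 3 months of treatment initiation in FLT3-ITD mutated patients with relapsed/refractory AML". Section 11.2 gives "The primary endpoint is the rate of CRc (CRc=CR/CRp/CRi) at any time during the first three cycles of therapy", and its next sentence adds "The CRc will be monitored with a time window of 3 months". Section 8.8 has "Response will be measured and defined for primary endpoints as the best response achieved during the first 3 cycles of therapy". The summary reports at the end of 11.3 take efficacy at the end of cycle 3.
- **Confirmation.** Section 8.0: "CRc rate is defined as the confirmed remission rate of all complete and incomplete CRs". No interval, repeat test or procedure for confirming is given anywhere. Section 8.8: "Best response is defined to be the best-measured response (CRc=CR+CRp+CRi, PR, or marrow clearance) post-treatment up to that time".
- **Early leavers.** Section 8.8 scores patients who stop before three cycles on their best response at the time they go off study. Section 11.3 treats patients who drop out before completing all the cycles as failures in the primary analysis. Section 5.3.1 plans up to 24 cycles, so it is not clear that all the cycles means three.

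Cycle length is not fixed. Section 5.1 sets 28 days plus or minus 7, allows a start from day 21 for patients with active disease, and allows delay for toxicity or other medical conditions.

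**The concern.** In a single-arm trial of 20 patients, the classification of each patient is the result. The primary estimate is a count of responders, and the futility rule in Table 4 is applied to such a count at 10 and 15 patients. If the text supports two answers for one patient, the count is not fixed before the data are seen. Whoever classifies late, single-measurement or early-leaving responders then chooses a definition, possibly knowing how close the trial is to a boundary. Section 11.2 also holds accrual when pending outcomes could decide a boundary, so the window determines how long such a hold lasts.

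**Working it through.** **1. The plan's own figures.** The inputs from 11.2 are the prior Beta(0.5, 1.5), a constant historical rate of 25%, a required gain of 25 points and a cut-off of 0.025. Futility is declared when Pr(p > 0.50 | Beta(0.5 + x, 1.5 + n − x)) < 0.025.

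| Responders / n | Posterior probability | Action |
|---|---|---|
| 2/10 | 0.0149 | stop |
| 3/10 | 0.0640 | continue |
| 4/15 | 0.0210 | stop |
| 5/15 | 0.0656 | continue |

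These match Table 4. With the Table 5 toxicity boundaries, and CRc and toxicity taken as independent, all 25 cells of Table 6 reproduce to about 0.0001. One of them is 0.1605 at true CRc 50% and toxicity 30%. The widest 95% credible interval at n = 20 is 40.4%, in line with the stated 41%. The calculations are sound; what is unsettled is the count that goes into them.

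**2. Length of the two windows.** Three months is 3 × 30.4375 = 91.3 days. Three cycles last:

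- 3 × 28 = 84 days, nominal
- 3 × 21 = 63 days, shortest
- 3 × 35 = 105 days, longest without delay.

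The second scheduled response marrow is on day 28 of cycle 3, plus or minus 7 (7.2.6). Its latest day is 28 + 28 + 28 + 7 = 91 on schedule, and 35 + 35 + 28 + 7 = 105 after two 35-day cycles. After one 8-week delay its nominal day is 28 + 56 + 28 + 28 = 140.

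**3. Patients classed both ways.**

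| Patient | One reading | Other reading |
|---|---|---|
| First CRc on day 105, in cycle 3 | Responder (8.8, endpoint sentence of 11.2) | Failure (1.1, monitoring sentence of 11.2) |
| 21-day cycles, first CRc on days 64 to 91 | Failure (three cycles) | Responder (3 months) |
| CRc at end of cycle 1, lost before a second assessment | Responder (8.8) | Unconfirmed (8.0) |
| CRc at end of cycle 1, then drops out | Responder (8.8) | Failure (11.3) |

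**4. Effect of one patient.** The final rate moves by 1/20 = 5 percentage points. At the looks, one patient turns 3/10 into 2/10, or 5/15 into 4/15, which is the difference between continuing and stopping. At the end, 10/20 gives a 95% credible interval of 27.7% to 68.1%, and 9/20 gives 23.7% to 63.8%. The lower limit therefore crosses the 25% historical rate on one patient, although the plan attaches no decision to that limit.

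**5. Sensitivity, by assumption only.** Suppose the stricter reading removes a share of responders, with CRc 50% under the broader reading and toxicity 30%. The documents give no such share.

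| Share of responders lost | CRc | Probability of early stopping |
|---|---|---|
| 0% | 50% | 16.1% |
| 5% | 47.5% | 18.9% |
| 10% | 45% | 22.6% |
| 20% | 40% | 32.2% |

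**The case against.** The strongest reply is that the two windows are meant as one. Section 11.2 uses them in consecutive sentences, and on schedule 84 days, or 91 with the marrow allowance, sits inside 3 months. Section 8.8 is written for primary endpoints, sections 8.1 to 8.3 ask for no repeat assessment, and *confirmed* may mean only documented. This stands for patients on schedule and limits how many are affected. It does not settle the others, because nothing says which wording prevails or what *confirmed* means.

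A reader might infer four stronger things, none of which the documents support.

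- **That delays are reserved for patients who benefit, so the cycle window is longest for responders.** Section 5.1.1.2 says "Delays in start of subsequent cycles greater than 8 weeks will be acceptable only for patients who are deriving clinical benefit". That restricts only delays beyond 8 weeks; shorter ones are open to any patient. Section 5.2.1 also plans no interruption for myelosuppression in the first 4 cycles.
- **That CRc is inflated against a 3-month benchmark.** The historical 25% in 11.2 carries no time window.
- **That a remission first seen at the end of cycle 3 cannot be confirmed in the window.** Section 7.2.6 allows extra marrows, and no text requires confirmation to fall inside the window.
- **That the chance of sitting one responder above the boundary is the chance of a changed decision.** The chance of exactly 3/10 is 12% at true CRc 50% and 25% at 35%. A change also needs a counted response to be reclassified. If each responder had a 5%, 10% or 20% chance of that (an assumption), the decision at 10 patients would flip with probability 2.0%, 4.5% or 11.3% at true CRc 50%, and 3.9%, 8.2% or 17.6% at 35%.

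**Conclusion.** The inconsistency is real and should be corrected before the first futility look. It has three parts: calendar against cycles, confirmed against best-measured, and best response at leaving against automatic failure. It is a contradiction in the primary endpoint, not missing detail, because the stated rules give opposite answers for patients the protocol expects or permits.

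The certain size is 5 percentage points per reclassified patient and one responder between continuing and stopping. The total effect depends on how many responses are late, seen only once or followed by early departure, and the documents do not say. Neither the direction nor the size of any bias can therefore be claimed. Nor do the documents tie Table 4 to the three-cycle count: 11.2 monitors over 3 months, while the summary reports use the end of cycle 3. Whether leaving for transplant counts as dropping out is also unstated. That matters because bridging to transplant is a secondary objective.

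**What to change.** Use one definition in sections 1.1, 1.2, 8.0, 8.8, 11.2 and 11.3, including the summary reports, and apply it to both the stopping rule and the final analysis. One workable version:

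- **Window:** CR, CRp or CRi on any assessment from cycle 1 day 1 through 3 months plus the existing 7-day marrow allowance (91 + 7 = day 98), whatever the cycle number.
- **Confirmation:** none required; delete *confirmed* from 8.0.
- **Early leavers:** scored on best response up to leaving, and failures only if no CRc was documented. Replace the dropout sentence in 11.3 accordingly.
- **Sensitivity analysis:** the three-cycle version of the endpoint.

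Day 98 is a choice, not something the documents dictate; another single window would also serve. Leave the marrow schedule unchanged. Moving the second marrow to a calendar date could separate it from the end-of-cycle-3 sample or add a procedure.

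The cost is a wording amendment. The sample size of 20 and the boundaries in Tables 4 and 5 do not change. The downside is that a few late responses, such as one first seen on day 105, would not count in the primary analysis, though they would appear in the sensitivity analysis.

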Several multitargeted tyrosine kinase inhibitors (TKIs) such as lestaurtinib, sunitinib, sorafenib, and midostaurin had activity against *FLT3* and have been investigated in *FLT3*-mutated AML. These agents have limited single-agent activity with marrow remission response rates of <10% with single-agent midostaurin(20) or sorafenib(21). On the other hand, second generation *FLT3* inhibitors such as quizartinib and gilteritinib have demonstrated potent anti-leukemic activity and improved outcomes in

patients with relapsed/refractory AML and *FLT3-ITD* mutations(22). About 40-50% of such patients achieve marrow responses to the second generation *FLT3* inhibitors such as quizartinib(23-25) and gilteritinib(26), with 20-30% bridged to allogeneic stem cell transplant. Although the response rates are high, the responses to both first and second generation *FLT3* inhibitors are invariably transient, lasting 8-18 weeks (except among patients who undergo transplantation) due to the emergence of resistance(27, 28). The primary cause of resistance is the acquisition of point mutations in the *FLT3* KD. Heidel et al first to identified point mutations in the *FLT3-ITD* KD as a mediator of resistance to the *FLT3* inhibitor midostaurin. They reported a single amino acid substitution at position 676 (N676K) within the *FLT3* KD as the sole cause of resistance to midostaurin in a patient with AML(29). Acquired point mutations in the KD may be preexisting or acquired after exposure to the *FLT3* inhibitors as has been shown with midostaurin(29). Homology modeling has identified two main types of *FLT3* mutations, namely TKD1 mutations involving the ATP-binding (hinge regions) and the TKD2 mutations involving the activation loop(30). Non-mutational mechanisms of resistance include up-regulation of compensatory pathways including the MAPK/ERK, *PI3K/Akt/mTOR*, *FOXO3A*, *SYK*, and *STAT5/PIM* pathways, up-regulation of the *FLT3* ligand or receptor, mutations in other kinases (e.g. *CBL*), activation of anti-apoptotic proteins *BCL2*, *MCL1* and *BCL-x(L)*, and tumor microenvironment mediated resistance(31, 32).

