The results of a randomized phase 2 trial comparing two lower doses of quizartinib have been reported (35, 36). In this trial, patients with relapsed or refractory AML with FLT3 mutation were randomized to receive quizartinib 30 mg or 60 mg orally, daily. A total of 76 patients were enrolled (38 to each arm). The overall composite response rate (CRc, which was the primary endpoint) was identical for the two arms (47%). The overall response rate was slightly higher with 60 mg daily (71%) than with 30 mg daily (61%) because of a higher rate of partial responses in the 60mg arm (24%) compared to the 30 mg arm (13%). QTc prolongation to >500 msec (the dose limiting toxicity for quizartinib) occurred in 3% with 60 mg and 5% with 30 mg. When comparing these results with a prior study (37) exploring higher doses (90 mg, 135 mg, and 200 mg) it is clear that the rate of CRc is identical at all dose levels with some increase in PR with progressively higher doses. However, QTc prolongation is clearly dose dependent and prolongations >60 msec from baseline occur in 40% or more of the patients treated at doses of 90mg or above, exceeding the threshold of acceptable grade 3 toxicity for the standard definition of MTD.

	2689-CL-2004	AC220-002 (Cohort 2)
--	--------------	----------------------

	30 mg/day (N = 38)	60 mg/day (N = 38)	90 mg/day (N=57)	135 mg/day (N=67)	200 mg/day (N=12)
Best Response					
CRc Rate	47%	47%	47%	45%	42%
PR Rate	13%	24%	25%	28%	50%
Maximum change in QTcF from baseline (msec)					
≤ 30	50%	44%	9%	9%	0%
> 30 to ≤ 60	47%	36%	46%	51%	8%
> 60	3%	19%	46%	39%	92%

In a recently reported phase I/II study, quizartinib and low intensity chemotherapy combination was shown to be safe and effective in patients with FLT3+ AML(38). In the phase I, patients with relapsed/refractory high-risk MDS, chronic myelomonocytic leukemia (CMML), or AML were eligible irrespective of FLT3 mutation and salvage status. The phase II enrolled patients age >60 years with untreated MDS/CMML/AML or patients of any age receiving first salvage treatment for AML with FLT3-ITD were eligible. Other requisites: performance status ≤2, adequate organ function and normal electrolytes (potassium, calcium and magnesium). Exclusions include: QTcF>450 msec, administration of drugs that prolong QT/QTc or strong CYP3A4 inhibitors or inducers.

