2.4 RATIONALE FOR STUDY

Second generation FLT3 inhibitors such as quizartinib and gilteritinib demonstrate potent anti-leukemic activity and improve outcomes in patients with relapsed/refractory AML with *FLT3-ITD* mutations(22). About 40-55% of FLT3-mutated patients not previously exposed to FLT3-inhibitors achieved marrow responses (CRc) to the second generation FLT3 inhibitors quizartinib(23-25) and gilteritinib(26), with 20-30% bridged to allogeneic stem cell transplant. Of note, recent FDA approval of midostaurin in combination with 7+3 induction chemotherapy in newly diagnosed FLT3-mutant AML signifies that essentially all relapsed FLT3-mutated AML patient will likely been exposed to at least one FLT3 targeting TKI. In this setting, the marrow response (CRc) rates with second generation FLT3 inhibitors such as crenolanib, gilteritinib and quizartinib have been reported to be lower than in prior FLT3 TKI naïve patients and are in the range of 20-25% (26, 48, 49) and Daiichi Sankyo unpublished communication).

Although response rates are high, the responses to single agent second generation *FLT3* inhibitors are almost invariably transient, maintained for 14-17 weeks, except among patients who undergo transplantation, due to the emergence of resistance(27, 28). The causes of resistance include the acquisition of point mutations in the *FLT3* KD (in 30-40% of resistant cases) and non-mutational mechanisms of resistance (in 50-60% of resistant cases) including up-regulation of compensatory pathways including the activation of anti-apoptotic proteins *BCL2*, *MCL1* and *BCL-x(L)*, *PI3K/Akt/mTOR*, *FOXO3A*, *SYK*, *RAS* and *STAT5/PIM* pathways, up-regulation of the *FLT3* ligand or receptor, mutations in other kinases (e.g. *CBL*), and tumor microenvironment mediated resistance(31).

[figure not shown]
MCL-1 was reported as an essential effector of *FLT3-ITD*-mediated drug resistance (50) and a number of *FLT3* inhibitors down-regulate *MCL1* thereby reducing the propensity to resistance to *BCL2* inhibitors. Combination of ABT-737 and *FLT3* inhibitors was synergistic in *FLT3-ITD*-mutated AML(51).

Furthermore, our recent data shows that *FLT3-ITD* activation/mutations may play a major role in primary and secondary resistance to ABT-199 (Popovic R, [name] et al, manuscript accepted to *American Journal of Hematology* May 2018). A phase 2 trial evaluated the efficacy and safety of venetoclax monotherapy in 32 patients with

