4.0 PATIENT SELECTION

Patients must have baseline evaluations performed prior to the first dose of study drug and must meet all inclusion and exclusion criteria. Results of all baseline evaluations, which assure that all inclusion and exclusion criteria have been satisfied, must be reviewed by the Principal Investigator or his/her designee prior to enrollment of that patient. In addition, the patient must be thoroughly informed about all aspects of the study, including the study visit schedule and required evaluations and all regulatory requirements for informed consent. The written informed consent must be obtained from the patient prior to initiating treatment or any study-specific procedures. The following criteria apply to all patients enrolled onto the study unless otherwise specified.

4.1 Inclusion Criteria:

A subject will be eligible for study participation if he/she meets the following criteria within 14 days prior to the first day of therapy.

1. FLT3-ITD mutated patients with relapsed/refractory AML (up to four prior therapeutic regimens for AML i.e. up to salvage 4 AML), including patients who may have been previously exposed to prior FLT3-inhibitor/s other than quizartinib (SCT or stem cell therapy for patients who previously underwent SCT/stem cell therapy in remission will not be considered a salvage regimen).
2. Patients must be ≥ 18 .
3. Eastern Cooperative Oncology Group (ECOG) Performance status of 0 to 2.
4. Potassium, magnesium, and calcium (normalized for albumin) levels should be within institutional normal limits.
5. Adequate hepatic (serum direct bilirubin $\leq 1.5 \times$ upper limit normal (ULN) (or $\leq 3.0 \times$ ULN if deemed to be elevated due to leukemia), alanine aminotransferase and/or aspartate transaminase $\leq 2.5 \times$ ULN (or $\leq 5.0 \times$ ULN if deemed elevated due to leukemia). Note: Subjects with documented Gilbert's Syndrome may have a total bilirubin $> 1.5 \times$ ULN.
6. Adequate renal function as demonstrated by a serum creatinine ≤ 1.8
7. Patients must provide written informed consent.

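### The 25% historical CRc comes from FLT3-inhibitor-exposed patients, but unexposed patients may enrol and no pre-specified analysis names exposure or gives them a reference rate

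*Combined protocol and SAP*

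**What the plan says.** Section 11.2 sets the comparator: "Thus, the historical data suggested a CRc rate of 25% for this population with quizartinib alone". The paragraph before it takes this from CRc rates of 20-25% with second-generation inhibitors in patients who had already received a FLT3 inhibitor, and notes that these are lower than in untreated patients. The reason for using the exposed rate is an expectation: "essentially all relapsed FLT3-mutated AML patient will likely have been exposed to at least one FLT3 targeting TKI". In the monitoring model, the CRc of the combination and the historical CRc "are assumed to follow a prior of Beta (0.5, 1.5) and a constant of 25%, respectively". The criterion for going on is: "The treatment will be considered worthy of further investigation if it elicits an increase in CRc to 50% or higher with acceptable toxicity".

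Inclusion criterion 1 in section 4.1 admits relapsed or refractory FLT3-ITD patients, "including patients who may have been previously exposed to prior FLT3-inhibitor/s other than quizartinib". Exposure is permitted but not required.

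The background gives a rate for unexposed patients. Section 2.4 states: "About 40-55% of FLT3-mutated patients not previously exposed to FLT3-inhibitors achieved marrow responses (CRc) to the second generation FLT3 inhibitors". Section 2.1 has a similar figure for the class: "About 40-50% of such patients achieve marrow responses to the second generation". Section 2.2 reports 47% for quizartinib alone at both 30 mg and 60 mg. Neither of these last two states prior exposure.

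Section 11.3 plans one overall CRc with a 95% credible interval, tests of unnamed covariates against response, and log-rank comparisons of time-to-event endpoints by unnamed subgroups. Section 6.1, in the optional correlative studies, mentions matched historical patients but lists no matching factors.

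**The concern.** In a single-arm trial the comparator carries the inference. A gain from 25% to 50% can be credited to venetoclax only if 25% is what these patients would have reached on quizartinib alone. The protocol's own figures put unexposed patients 15 to 30 points higher (40 - 25 and 55 - 25), so a mixed sample has a no-effect rate above 25%. The same mix also weakens the futility rule, because the Table 4 boundaries are derived from 25% plus 25 points.

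The link between the exposed rate and the enrolled patients is an expectation that the plan never checks. As written, the report could give one CRc against 25% without saying how many patients belonged to the population behind the 25%.

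**Working it through.** **Inputs from the documents.** Phase II N = 20; historical CRc 25%; prior Beta(0.5, 1.5); futility stop at 2 or fewer of 10, or 4 or fewer of 15 (Table 4); toxicity stop at 4 or more of 5, 6 or more of 10, or 8 or more of 15 (Table 5); exposed CRc 20-25% (section 11.2); unexposed CRc 40-55% (section 2.4).

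**Assumptions.** The unexposed share *s* is not given, so a range is shown. Reaching 50% is read as at least 10 of 20. Exposure is taken as random over enrolment order. Toxicity stopping is ignored except in the check of Table 6.

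**Step 1: reproduce the plan.** The futility rule stops when Pr(CRc > 0.50 | data) < 0.025. With x responses in n patients the posterior is Beta(0.5 + x, 1.5 + n - x). The tail above 0.50 is 0.0149 at 2/10 and 0.0640 at 3/10, then 0.0210 at 4/15 and 0.0656 at 5/15. This gives the Table 4 boundaries. Exact binomial recursion through these looks gives a futility-stop probability of 0.7186 at a true CRc of 25% and 0.0831 at 50%. The Table 5 looks at a 30% DLT rate give a probability of not stopping of 0.9156. Assuming independence:

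- CRc 25%: 1 - 0.9156 × (1 - 0.7186) = 0.7424
- CRc 50%: 1 - 0.9156 × (1 - 0.0831) = 0.1605

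Both match Table 6. The arithmetic is sound given 25%; the question is only the reference rate.

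**Step 2: no-effect CRc in a mixed sample.** With exposed rate *e* and unexposed rate *u*, p = e(1 - s) + u·s. At e = 0.25, the lower and upper values below use u = 0.40 and u = 0.55. For example, s = 0.20 gives 0.25 × 0.80 + 0.40 × 0.20 = 0.28 and 0.25 × 0.80 + 0.55 × 0.20 = 0.31.

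| Unexposed share | No-effect CRc | Futility stop | Passes both looks and reaches 10/20 |
|---|---|---|---|
| 0% | 25% | 71.9% | 1.4% |
| 10% | 26.5-28% | 67.2-62.3% | 2.1-3.0% |
| 20% | 28-31% | 62.3-52.5% | 3.0-5.9% |
| 50% | 32.5-40% | 47.6-25.9% | 7.8-24.3% |

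With u = 0.47 the last column is 2.5%, 4.2% and 14.1% at 10%, 20% and 50% unexposed.

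**Step 3: margin in the 25%.** If the exposed rate is really 20%, the pooled no-effect rate reaches 25% when s = 0.05/(u - 0.20). That is 25.0% for u = 0.40 and 14.3% for u = 0.55. At 20% unexposed the chance of reaching 10/20 is then 1.0-2.4%.

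**Step 4: would the generic covariate test be enough?** Suppose Fisher's exact test in section 11.3 were applied to exposure (two-sided 5% assumed; true CRc 25% against 40-55%). Its power is 2-4% with 2 unexposed of 20, 5-14% with 4 and 4-13% with 10. A non-significant result would not show the mix to be harmless.

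**The case against.** The strongest reply is that the plan states its premise openly, and under that premise the effect is slight. At 10% unexposed the chance of reaching 10/20 moves only from 1.4% to 2.1-3.0%. The larger figures need half the patients to be unexposed, which no part of the documents supports. The plan also took the top of the 20-25% range, which absorbs modest mixing (step 3). These points stand and limit the size of the concern. They do not remove it, because nothing commits the plan to showing which case applied.

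The threshold of 10 of 20 is an interpretation. Section 11.3 plans estimation only, so the probabilities above are not error rates of the plan. This also stands.

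The evidence for a high unexposed rate can be questioned. In the phase 1 quizartinib study in section 2.2, FLT3-ITD patients had 3 CRi, 1 CRp and 1 CR among 18, a CRc of 5/18 = 28%. The 47% trial does not state exposure, and its best-response figure gives no time window, whereas this trial counts CRc within three cycles. Applying 40-55% directly may therefore overstate the no-effect rate. But the phase 1 study was dose-escalation and does not state exposure either, so it does not displace the one range the protocol gives explicitly for unexposed patients. The uncertainty is a reason to show a range.

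Finally, the covariate tests could include exposure. They do not name it, and they supply no reference rate, which is what the comparison lacks.

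**Conclusion.** The concern holds. The comparator describes exposed patients, eligibility is wider, and no pre-specified analysis names exposure or gives unexposed patients a reference. On the protocol's own rates the consequence is small if exposure is nearly universal and material only if a large share is unexposed: 2.1-3.0% at 10% unexposed against 7.8-24.3% at 50%, from a base of 1.4%. These figures rest on an assumed unexposed share, no venetoclax effect, an exposed CRc of 25%, an unexposed CRc of 40-55%, and the reading of the criterion as at least 10 of 20. If the exposed CRc is nearer 20%, the plan has some margin. This should be fixed because the remedy is cheap; the design need not be reworked.

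**What to change.** Leave Tables 4 to 6, eligibility, sample size and the 50% criterion unchanged. Add to section 11.3:

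> The number of patients with and without prior FLT3-inhibitor exposure will be reported. CRc with its 95% credible interval will be reported for all patients and separately by prior FLT3-inhibitor exposure. As a supportive analysis, the overall CRc will also be shown against a reference weighted by the enrolled exposure mix (25% for exposed; 40% to 55% for unexposed, shown as a range), and the excess over 25% will be interpreted in light of that mix.

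With 1, 2, 4 or 10 unexposed of 20, that reference would be 25.8-26.5%, 26.5-28%, 28-31% or 32.5-40%.

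The cost is three sentences and one tabulation. Prior therapy is already reviewed for eligibility, since section 4.1 limits prior regimens and section 4.2 excludes prior quizartinib. The drawbacks are small strata and a slightly less favourable reference if unexposed patients enrol. At an observed CRc of 50%, with the plan's Beta(0.5, 1.5) prior, the 95% credible interval is 40 points wide for all 20 patients (27.7-68.1%), 42 for 18 exposed and 44 for 16 exposed, so little precision is lost in the main group. An unexposed group of 4 (70 points) or 2 (78 points) would be descriptive only.
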